## 1. Study summary

Study Title	Safety of laparoscopic ChOlecystectomy performed by Trainee surgeons with different CHolangiographic techniques (SCOTCH)
Internal ref. no. (or short title)	SCOTCH study
Study Design	Multicenter prospective interventional trial
Study Participants	Patients
Endpoints	Primary endpoints Time to reach CVS with the utilisation of three different intraoperative imaging modality during LC performed by ST
Summary of eligibility criteria	
Inclusion Criteria
 
 
- Patient scheduled for elective laparoscopic cholecystectomy
 
- Patient age <math>\geq</math> 18 years
 
- Patient able to give consent to the procedure
 
 
Exclusion Criteria
 
 
- Open cholecystectomy
 
- Emergency laparoscopic cholecystectomy
 
- Allergy towards iodine, lohexol or indocyanine green
 
- Liver or renal insufficiency
 
- Thyrotoxicosis
 
- Pregnancy or lactation
 
- Legally incompetent for any reason
 
- Withdrawal of inclusion consent at any time
 
- Age outside inclusion range
 

Arms of the study	
Group CVS-WL (control group): the CVS is achieved in white light, without the utilization of an intraoperative imaging technique. CVS in white light was selected as the control group since it constitutes the actual recognized standard in clinical practice.
 
Group IOC: the CVS is achieved with the help of intraoperative cholangiography
 
Group NIR-C: the CVS is achieved with the help of near-infrared fluorescence cholangiography

Version and date of protocol amendments	Vers. n.1.1- 15/11/2020
Clinicaltrials.gov Registration number	NCT04863482

## 3. Glossary of Terms

**LC**= laparoscopic cholecystectomy

**ST**= surgical trainee

**CVS**= critical view of Strasberg

**IOC**= intraoperative cholangiography

**NIR-C**= Near-infrared fluorescence cholangiography

**CBD**= common bile duct

**BDI**= bile duct injury

#### 4. Background

Laparoscopic cholecystectomy (LC) gained popularity among general surgeons in 1990s and rapidly become one of the most commonly performed procedures in digestive surgery [1, 2], with more than one million cholecystectomies being performed in the United States per year [3]. LC remains also one of the most commonly performed procedure by general surgeons during the training period [4, 5].

Even if previous report LC cases performed by surgical trainees (ST) are not associated with higher operative morbidity [6], the length of operative time is significantly increased when compared with that of LC cases performed by attending surgeons, due, most of all, to difficulties in identifying the anatomical structures [7, 8], and this sometimes leads to an attending surgeon taking away the case from the trainee.

Furthermore, despite the fact that LC has proven to be a safe procedure, the rate of common bile duct (BDI) injury still remains unacceptably high even in the hands of minimally invasive trained surgeons [9] ranging from 0.2 to 1.5% in individual reports [10, 11-14], much higher than initial reports [14, 15], associated with significant morbidity and mortality, lower quality of life and increased costs, related to additional health care measures, loss of work days, and insurance claims [2,10, 16, 17]. Way et al reported that, in 97 % of cases, non-technical errors, predominantly relating to perceptual errors, in which the operator was led to make false assumptions regarding the position of the bile duct in relation to the anatomy at hand, were at the root cause of the injury. [18] From these observation many of the existing recommendations to avoid BDI insist on the importance of the establishment of the critical view and understanding the relevant anatomy, aided by adequate retraction and visualization. [19]

The correct identification of Calot's triangle, sometimes hard even in expert hand, may be particularly challenging for ST leading at those misidentification of the structures that are the most frequent causes of BDI during LC as previously stated. As a matter of fact, the most frequent site of CBD injury is below the bifurcation of the right and left hepatic ducts (65 %), and once anatomic confusion has led the surgeon astray, injury tends to occur in relatively predictable locations along the biliary tree [4]

With laparoscopic surgery, there is also loss of haptic input and stereoscopic depth perception, which predisposes to the misperception that leads to BDI [20] Various methods have been described to help the identification of the structures in Calot's triangle; these include intraoperative cholangiogram (IOC) [22], critical view of safety (CVS) [23] and the near-infrared fluorescent cholangiography (NIRF-C) [24].

Each of these technique have been proved to be useful and, at the same time, to have some intrinsic drawback that could be amplified when in unexperted hands.

The use of IOC during LC is well established [25] with the aim to detect of bile duct stones, defining biliary tree anatomy and the early recognition of iatrogenic common bile duct (CBD) injuries. [26-29]

Although regarded as a safe procedure with a low risk of complications, the merits of routine IOC usage remain an area of debate. Some studies suggest that it adds significant operating time and cost, without reducing the risk of detection of retained CBD stones or bile duct injury. [30-33] Others

demonstrated that the routine use of IOC for cholecystectomy plays a crucial role in the detection of intraoperative CBD stones and CBD injury.

It could be argued, however, that to perform IOC it is necessary to incise what is presumed to be the CD, which in itself may be the cause of a lateral injury of the CBD (or CHD) in case of mistaken anatomy [30] and, in a training setting, IOC can be difficult to teach and residents do not gain enough experience with it as not all surgeons perform it routinely and that [1]

The CVS, more than a technology the others, is a technique, introduced by Strasberg and Brunt in 1995, [23] and it is considered the gold standard to perform a safe cholecystectomy with identification of biliary structures (eg, cystic duct, common hepatic duct, and common bile duct) during dissection. Three criteria are required to achieve the CVS: (1) the hepatocystic triangle must be cleared of adipose and fibrotic tissues; the common bile duct and common hepatic duct must not be exposed; (2) the lower third of the gallbladder must be separated from the liver bed to expose the cystic plate; and (3) 2 and only 2 structures should be seen entering the gallbladder. In this case, the main drawback for ST is the necessity to dissect around the Calot's triangle to demonstrate the CVS. It can become challenging for an attending surgeon to supervise the resident to dissect and demonstrate CVS without any visual landmarks.

The most recently introduced intraoperative imaging technique is the near-infrared fluorescent cholangiography (NIRF-C), described by Ishizawa et al in 2009. [24] The NIRF-C allows a real-time enhanced visualization of the extrahepatic biliary tree by fluorescence. NIRF-C is based on the administration of a fluorophore, the indocyanine green, which is excreted in the biliary system, and on the use of a nearinfrared light source, exciting the fluorophore and enabling the visualization. NIRF-C offers some clear advantages when compared with the conventional cholangiography (real-time visualization of biliary tree, reduced costs, easy learning curve, lack of X-ray exposure, safer dissection of Calot's triangle, and possibility to associate fluorescent angiography to highlight vessels). [34, 35] Additionally, NIRF-C has shown a good potential as a teaching tool for trainees. [1, 36]

Previous report demonstrated the feasibility and safety of NIRFC [37]. Prospective study comparing IOC and NIRFC, that the latter is associated with a shorter duration of operation [38] and confirmed its non-inferiority to IOC to X-ray cholangiography in visualizing the critical junction during LC. [39]

Unfortunately, however, as confirmed the EURO-FIGS registry on fluorescence-guided surgery, there is a wide disparity in terms of protocols for NIRFC, across several European surgical centers, particularly in terms of ICG dose and timing of administration. [40]

The aim of this study is to address which of the techniques now available could be addressed as the best option in a training setting to enhance the learning curve, to ideally build a safe cholecystectomy training program and virtually eliminate the risk of BDI due to anatomic misinterpretation during the training period.

## **5. Patients and study design**

### **5.1 Study design**

The study will be a multicentre prospective observational study. Members of the Italian Society of Endoscopic Surgery [SICE] will be invited to participate. All participating centers will be required to register the study according to local regulations. Evidence of successful registration should be sent to your national network committee prior to beginning of data collection.

### **5.2 Study groups**

The enrolled patients will be divided into three groups, 1 control group and 2 treatment groups, according to the selected technique to achieve the CVS during LC:

**Group CVS-WL (control group):** the CVS is achieved in white light, without the utilization of an intraoperative imaging technique. CVS in white light was selected as the control group since it constitutes the actual recognized standard in clinical practice.

**Group IOC:** the CVS is achieved with the help of intraoperative cholangiography

**Group NIR-C:** the CVS is achieved with the help of near-infrared fluorescence cholangiography

### **5.3 Rationale for Study Design**

Since to date there is no consensus on which is the best technique to correctly identify the anatomy of the Calot's triangle during LC performed by ST, this trial would aim to propose a standard technique to be used in this peculiar setting.

### **5.4 Potential Benefit for Patients**

In teaching hospitals and, more generally in a training setting, overcoming the problem of providing high surgical quality while educating ST can be challenging. This may change in the future if residents are able to better identify the anatomy with IOIFC, shortening the learning curve and improving the safety profile of LC, that, in a clinical point of view, would translate into a shorter operative times and reduction of the potential risk of BDI.

### **5.5 Patient Risk**

There are no additional risks on the participation of this study as no additional procedures are being performed to clinical guidance. In accordance with standard care, patients shall receive written information regarding the index procedure.

## **6. Study objectives**

### **6.1 Primary Outcomes**

The primary objective is to compare NIFC, IOC and CVS-WL for identification of the junction between the cystic duct, the common hepatic duct and the CBD during LC performed by general surgery trainee always supported by an expert surgeon. The technique will be considered successful when the CVS will be achieved. The time to achieve the CVS will be recorded by an independent surgeon who will be present in the operative room during the procedure.

The definition of trainee will be on the number of the procedures performed before the beginning of the study. Surgeons who performed less than 30 procedures before the beginning of the study, since learning curve studies have determined the steep portion to consist of 10 to 30 operations [40–43]. The operating surgeon will complete a structured questionnaire focusing on anatomical identification of the bile ducts immediately after each operation (**Appendix A**) and a more generic

questionnaire on task load. (**Appendix B**) The surgeon's satisfaction score will be given on a subjective visual analogue scale ranging from 1 to 5 (1 = not satisfied, 5 = extremely satisfied). (**Appendix C**)

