## **8. Study procedures**

### **Critical view of Safety(CVS)**

The CVS has 3 requirements. First, the triangle of Calot must be cleared of fat and fibrous tissue. It does not require that the common bile duct be exposed. The second requirement is that the lowest part of the gallbladder be separated from the cystic plate, the flat fibrous surface to which the non peritonealized side of the gallbladder is attached. The cystic plate, which is sometimes referred to as the liver bed of the gallbladder, is part of the plate/sheath system of the liver. The third requirement is that 2 structures, and only 2, should be seen entering the gallbladder. Once these 3 criteria have been fulfilled, CVS has been attained). The rationale of CVS is based on a 2-step method for ductal identification that was and continues to be used in open cholecystectomy. First, by dissection in the triangle of Calot, the cystic duct and artery are putatively identified and looped with ligatures. Next, the gallbladder is completely dissected off the cystic plate, demonstrating that the 2 structures are the only structures still attached to the gallbladder. Time consumption and includes the period from the initial dissection and the obtaining of an acceptable view according to the previously described criteria in order to safely transect the cystic duct.

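### The primary endpoint is time to CVS in the summary, but Section 6.1 makes it junction identification judged by a yes/no CVS rule that does not measure the junction

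*Protocol*

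**What the plan says.** - **Protocol, Section 1 (Study summary).** The only variable labelled a primary endpoint is a time: "Time to reach CVS with the utilisation of three different intraoperative imaging modality during LC performed by ST".
- **Section 6.1 (Primary Outcomes).** The primary objective compares the three techniques for "identification of the junction between the cystic duct, the common hepatic duct and the CBD during LC performed by general surgery trainee". The rule for success follows: "The technique will be considered successful when the CVS will be achieved". Time then appears as something measured: "The time to achieve the CVS will be recorded by an independent surgeon".
- **Section 6.3.** Time to obtain a CVS is item x in a list of evaluated parameters. The duration of cholangiography is a separate item, ix.
- **Section 4 (Background) and Section 8 (Critical view of Safety).** Both give the same three CVS criteria: a cleared triangle, the lower gallbladder separated from its bed, and two structures only entering the gallbladder. On the main ducts, Section 4 says "the common bile duct and common hepatic duct must not be exposed" and Section 8 says "It does not require that the common bile duct be exposed".
- **Section 9.1 (Sample size).** Three calculations are given, with rates of 80% and 90%, 20% and 30%, and 60% and 91%.

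**The concern.** A trial needs one stated variable on which its main conclusion rests. Here a reader of Section 1 expects a comparison of times, a reader of Section 6.1 expects a comparison of success rates, and a reader of Section 9.1 finds only rates. The results could favour different techniques: one might reach CVS more often but more slowly. The protocol does not say which would count, so the choice could be made after the data are seen. A later analysis plan cannot cure this alone, because the protocol itself names conflicting endpoints.

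The second problem is validity. If success means CVS achieved, a high success rate does not show that trainees identified the junction, which is the stated objective.

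**Working it through.** **1. The variable in each place**
- Section 1: time to CVS (continuous).
- Section 6.1, objective: junction identified.
- Section 6.1, success rule: CVS achieved, yes or no.
- Section 6.1, last role: time to CVS, recorded.
- Section 9.1: proportions only.

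These are different variables, and no sentence ranks them.

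**2. Does the success rule measure the objective?** None of the three CVS criteria mentions the junction of the cystic duct with the common hepatic and common bile ducts. The third is about the gallbladder end: "The third requirement is that 2 structures, and only 2, should be seen entering the gallbladder". A patient can meet all three, count as a success, and never have had the junction shown.

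**3. What the forms record (Appendix A).** The white-light form asks whether the CVS was reached and has no junction item. The IOC form asks whether the cannulated duct is the cystic duct. The NIR-C form asks about the junction and has no CVS item. On these forms, neither CVS success nor junction identification is captured in all three arms.

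**4. The clock (Section 8).** White light and NIR-C are timed from initial dissection. IOC is timed from application of the grasper, which comes after the cystic duct has been dissected. The IOC interval may be meant as the duration of cholangiography (Section 6.3, ix). In that case the IOC arm has no stated start for time to CVS at all. Either way, time is not comparable across arms as written.

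**5. What the stated sample size rests on.** Inputs from Section 9.1: 80% for IOC, 90% for fluorescence, a 10-point margin, one-sided 5%, 60 per group, 90% power.
- n = (z0.95 + z0.90)² × [p1(1−p1) + p2(1−p2)] / (p2 − p1 + margin)² = (1.645 + 1.282)² × (0.16 + 0.09) / 0.20² = 53.5, so 54 per group.
- Power at 60: SE = √(0.25/60) = 0.0645; 0.20/0.0645 − 1.645 = 1.45, giving 92.7%.
- Exact enumeration at 60 gives 92.5% to 93.0% for three common tests and 89.6% for a continuity-corrected Wald test. The protocol does not name its test; the last variant reproduces 60 per group with 90% power.
- 20% against 30%, two-sided 5%, 80% power: 294 per group, against 300 stated.
- 60% against 91%, two-sided 5%, 95% power: (1.960 + 1.645)² × (0.24 + 0.0819) / 0.31² = 43.5, so 44, as stated per group.

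All three are calculations for a yes/no outcome. None uses time.

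**6. What 60 per group means for time.** The protocol gives no mean, SD or target difference for time, so a required number cannot be derived from it. The detectable standardised difference can. For one two-sided 5% comparison it is √(2/n) × (z0.975 + z_power):
- 80% power: √(2/60) × (1.960 + 0.842) = 0.51.
- 90% power: √(2/60) × (1.960 + 1.282) = 0.59.
- 90% power, Bonferroni for three pairs: 0.67.

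Conversely, for assumed standardised differences of 0.3, 0.5, 0.6 and 0.8, one comparison at 90% power needs 234, 85, 59 and 33 per group. These figures assume a time for every patient and a scale on which means can be compared.

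**The case against.** Section 6.1 can be read as a chain: the junction is the aim, CVS is its working criterion, and time is the measurement. Section 4 supports this by linking CVS to identification of the cystic, common hepatic and common bile ducts. In addition, not exposed by dissection is not the same as not identified. This has some force. It makes it uncertain that junction identification was ever meant as a separate primary test. It does not reconcile a time in Section 1 with a yes/no rule in Section 6.1 and proportions in Section 9.1, and the three criteria still do not require the junction to be shown.

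Three stronger conclusions are tempting, but the protocol does not support them.
- **A false-positive risk near 10%.** Two independent 5% tests give 1 − 0.95² = 9.75%. The protocol states no rule by which either result could carry the claim, and two outcomes built on the same CVS event are unlikely to be independent.
- **That 10% to 20% of patients would have no time.** The 80% and 90% in Section 9.1 are success rates for two cholangiographic techniques. They are not said to be CVS rates, and no white-light rate is given. A patient who never reaches CVS still has time observed up to conversion or abandonment, which is a question of censoring.
- **That the junction comparison is decided by design against white light.** Not requiring exposure does not mean the structures cannot be seen.

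The choice of time over success is also open to argument, since Sections 6.1 and 9.1 lean towards a rate. What is essential is one endpoint, used consistently.

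**Conclusion.** The concern stands as a contradiction within the protocol, together with a narrow mismatch between the success rule and the objective. Sections 1, 6.1 and 9.1 do not agree on what decides the trial, and meeting the CVS criteria does not demonstrate the junction. This must be fixed before any confirmatory claim can rest on the trial.

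Its size is best expressed through the sample size: the one variable labelled a primary endpoint has no sample-size basis. At 60 per group, only a difference of roughly half an SD or more would be detected with 80% power. That figure assumes one two-sided 5% comparison and complete times. Any translation into minutes needs an SD that the protocol does not give.

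**What to change.** - Name one primary endpoint and state it identically in Sections 1, 6.1, 9 and 9.1. Time to CVS is the natural choice, because it is the only variable labelled as such. Make CVS achieved (yes/no) a secondary endpoint.
- In Section 8, start the clock for time to CVS at initial dissection in all three arms, with one common stopping event. Keep the duration of cholangiography as a separate variable.
- State how patients in whom CVS is not reached are counted, for example as censored at conversion or abandonment, and match the method in Section 9. Its t-test and Wilcoxon test do not handle censored times, and it assigns Kaplan-Meier only to survival and recurrence outcomes.
- Delete the Section 6.1 sentence that equates CVS with success. List junction identification as a separate secondary outcome, and reconcile the Section 4 and Section 8 wordings on exposure of the ducts.
- Put the same CVS and junction items on every arm's Appendix A form.
- Restate Section 9.1 for the chosen endpoint, with a sourced SD and target difference. If 60 per group is kept, state the detectable standardised difference from step 6.

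The cost is small: protocol and form wording, a few added form items and a restated justification. It grows only if the target difference for time turns out to need more patients than planned.

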### **9.3 Expected Duration of Trial**

The trial is expected to run for 6 months (time from first patient recruitment to last patient evaluation). Data analysis will take a maximum of 3 months after this time.

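### Operator experience is set once, at study start, and is not listed as recorded at each operation, so differences in experience between technique groups could be mistaken for a technique effect on time to CVS.

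*Protocol*

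**What the plan says.** - **Who counts as a trainee (section 6.1).** "The definition of trainee will be on the number of the procedures performed before the beginning of the study". Those who qualify are "Surgeons who performed less than 30 procedures before the beginning of the study", with no lower bound. The reason given is that "learning curve studies have determined the steep portion to consist of 10 to 30 operations". The protocol does not reassess status later and sets no cap on cases per trainee.
- **Primary endpoint (section 1).** "Time to reach CVS with the utilisation of three different intraoperative imaging modality during LC performed by ST".
- **Experience and time (section 4).** For trainees, "the length of operative time is significantly increased when compared with that of LC cases performed by attending surgeons". The protocol puts this down mainly to difficulty in identifying the anatomy.
- **How groups arise (sections 5.1 and 5.2).** Patients are divided "according to the selected technique to achieve the CVS during LC". Section 5.1 calls the study observational, while the summary calls it interventional. Neither section states randomisation, an order of techniques or balancing within surgeon.
- **Comparison (section 9).** Continuous variables are compared by Student's t-test or Wilcoxon, with no term for operator or experience.
- **Data listed (section 6.3, Appendix A).** The thirteen parameters and the three technique questionnaires include neither the operator's identity nor the operator's case number.
- **Duration (section 9.3).** "The trial is expected to run for 6 months". Section 7 recruits consecutive eligible patients.

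**The concern.** The reason for the limit concerns how experienced the operator is when operating, but the rule measures experience only on the day the study starts. Two operations that both count as trainee cases may be an operator's second and fiftieth. That spread matters because the endpoint is a duration and, by the protocol's own account, trainees take longer chiefly because of the anatomical task being timed.

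A spread in experience biases the comparison only if it differs between technique groups. With technique selected and not allocated, nothing in the protocol prevents this. One centre's trainees may be further along than another's, or a technique may be taken up later, once trainees have gained practice. An unadjusted two-sample test would assign the whole difference to technique. The study aims to name the best technique for training, so that error would go straight into its main conclusion.

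**Working it through.** The plan gives no figure of its own on this point beyond the limit of 30, so there is nothing to reproduce. The checks below ask what the listed data allow and how large the issue could be.

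**1. What could be adjusted for.** Adjustment needs the operator's case number at each operation, or the operator's identity, the prior count at entry and the sequence of operations. Section 6.3 lists patient, procedure, outcome and surgeon-rating items. Appendix A asks about image quality, identification and willingness to transect. A later analysis plan could not build the covariate from these lists.

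**2. Share of operations past case 30.** Let a trainee enter with *b* prior cases and do *k* operations in the study. The operations past case 30 number max(0, *b* + *k* − 30).

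- *b* = 29: the first study operation is case 30 and the second is case 31. The share is (*k* − 1)/*k*: 4/5 = 80%, 9/10 = 90%, 19/20 = 95%.
- *b* = 20: 0/10 = 0%, 10/20 = 50%, 20/30 = 67%.
- *b* = 10: 0/20 = 0%, 10/30 = 33%.
- *b* = 0: none up to *k* = 30.

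If *b* is spread evenly over 0 to 29 (an assumption) and *k* ≤ 30, the counts past 30 sum to 1 + 2 + … + (*k* − 1) = *k*(*k* − 1)/2 over 30*k* operations. The share is therefore (*k* − 1)/60.

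| Study cases per trainee, *k* | Share past case 30 |
|---|---|
| 5 | 4/60 = 7% |
| 10 | 9/60 = 15% |
| 20 | 19/60 = 32% |
| 30 | 29/60 = 48% |

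**3. Which *k* is plausible.** The protocol gives no number of trainees. Section 9.1 contains group sizes of 60 and of 300, that is 180 or 900 patients over three groups. With 10 trainees (assumed), *k* averages 180/10 = 18 or 900/10 = 90. With 50 trainees (assumed), it averages 180/50 = 3.6 or 900/50 = 18. The documents do not narrow this range.

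**4. Can learning alone look like a technique effect?** Take an assumed curve in which relative time at case *c* is 1 − 0.4 × (1 − e^(−*c*/15)), with no true difference between techniques and 30 study cases per trainee. Mean relative times for the three techniques are:

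| Prior cases | Used in consecutive blocks of 10 | Interleaved |
|---|---|---|
| 0 | 0.882 / 0.745 / 0.674 | 0.778 / 0.767 / 0.756 |
| 29 | 0.641 / 0.621 / 0.611 | 0.626 / 0.624 / 0.623 |

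From 0 prior cases in blocks, the last technique looks (0.882 − 0.674)/0.882 = 24% faster than the first. From 29 prior cases the figure is (0.641 − 0.611)/0.641 = 5%. Interleaved, it is (0.778 − 0.756)/0.778 = 3% from 0 prior cases, and under 1% from 29.

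So bias can arise from learning alone. It depends mainly on how techniques are spread over each operator's cases, and it is largest on the steep early part of the curve, below case 30.

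**The case against.** Fixing operator status at entry is a legitimate choice. Because section 6.1 defines trainees by their count before the study, later operations by the same surgeons lie inside the defined population. A reader might infer that the analysed population drifts away from the one defined. The text does not support that: what changes is experience within the population.

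A reader might also infer that many operations lie well beyond case 30. That needs a case volume which the protocol does not give. With many trainees doing few cases each, the share is small. Nor do the documents say that any technique is used later than another, so no direction of bias can be asserted. If techniques are interleaved within operators, learning mainly adds variance.

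Reapplying the limit at each operation is not the cure either, since the mixing is strongest below case 30. All of these points stand.

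Two further objections stand in part. Section 6.3 may not be the complete dataset: conversion and intensive care stay are outcomes in section 6.2 but are missing from 6.3. Each operator's prior count must also be established to apply the 6.1 rule. The claim is therefore limited to the listed data. Secondly, covariate models and sensitivity analyses are commonly left to an SAP. But an SAP cannot adjust for a variable that was not collected, and the data list is in this protocol.

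**Conclusion.** The point holds as a gap in data collection and adjustment. Experience is assessed once, technique is selected, the stated test is unadjusted, and the listed data carry neither operator identity nor case number. A difference in experience between technique groups could therefore be taken for a technique effect and could not be separated from it using those data.

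The size and direction of the bias are unknown. The range of about 7% to 48% of operations past case 30 rests on even prior counts and 5 to 30 study cases per trainee. It describes how far experience may spread and does not measure bias. The spurious difference of 24% comes from an assumed curve with techniques used in consecutive blocks; interleaving reduces it to 3%. These figures show that the problem can matter, not that it will. The change should be made before data collection, because the missing fields may be hard to recover afterwards.

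**What to change.** - Add two items to section 6.3: a coded operator ID, and the number of LCs performed by the operator before this operation.
- In section 9, replace the two-sample test for time to CVS with a model that contains technique and that count, and that accounts for clustering by operator. The count should be allowed a non-linear effect, since the protocol itself describes a steep phase.
- Keep the entry definition of trainee. Optionally, add a sensitivity analysis restricted to operations up to the operator's 30th.

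The cost is two extra data fields, a somewhat more complex analysis and fewer cases in the sensitivity analysis. Adjustment does not replace randomisation: differences between operators other than case count can remain mixed with technique where an operator uses only one technique.
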